Upon the verification of eligibility, the remaining clinician-rated assessments will be completed (i.e. the modified MDS-UPDRS part III, the MDS-UPDRS part IV, the Non Motor Symptom Scale (NMSS), the MRI safety screen, COVID-19 related screening questions). A bilateral ear exam will be performed for eligible subjects. A bilateral ear exam may be performed for

subjects who are not eligible. If any ear abnormalities are noted during the ear exam (including pain, infection, damage/injury, or excessive earwax), it will be the participant's responsibility to resolve it before continuing in the study. If the subject chooses not to resolve any ear issues, including earwax removal, he/she will be excluded. The handout/guide listing the contact information to for study staff should participants have any questions or experience any AEs during the duration of the study will be reviewed. The clinical research coordinator will then confirm that the participant has received the patient reported outcomes (PROs) including the Geriatric Depression Scale (GDS), the Parkinson's Anxiety Scale (PAS), the Epworth Sleepiness Scale (ESS) and the Functional Assessment of Chronic Illness Therapy – Fatigue (FACIT-F). Participants will be asked to complete these assessments at the end of the virtual visit and reminded that they should complete the forms when in the “On” medication state and to bring them to their scheduled clinic visit.

*Note, visits for the baseline, end of treatment and post treatment follow-up should be set up for the same time of day so as to minimize variability that may result from the fluctuating kinetics of responses to dopamine replacement therapies. Care should also be given to minimize the duration of time between the remote clinical visits and the imaging visits making these next day if possible. If the same time of day is not possible, then it is ideal to schedule visit at a time that is the same relative to the scheduled dopamine replacement therapy.

Baseline imaging / Device training visit:

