After the completion of the MRI scan, the coordinator will accompany the study participant to the clinic for TCD recordings. There, the participant will receive a second hypercapnia challenge (using the same conditions described above) while undergoing TCD recording. Pulse wave velocity (PWV) may be measured at this time.

Treatment period:

All participants will treat twice daily, at least one hour apart. Each treatment duration is 19 minutes 39 seconds. Participants will only wear the device when administering a treatment per protocol. The treatment period is anticipated to last for 12 weeks. However, treatment may be

extended for approximately 2 additional weeks in the case of scheduling conflicts (such as those imposed by standard operating procedures imposed by WFU to limit the spread of COVID-19). Patients should continue to treat twice daily up until the time of the end of treatment clinic visit.

Interim phone calls:

- Participants will be called the next day after their Device training visit to confirm that participants were able to successfully administer treatment in the home setting.
- Scheduled follow up phone calls will be made at week 3, week 6 and week 9. During these calls, the coordinator will ask about any adverse events, any changes to concomitant medications and to confirm no issues have arisen with use of the Device.
- Participants will also have received the contact information for the site coordinator so that they may report potential adverse events or issues with the Device in real time.

End of treatment visit (remote) – week 12:

During this remote visit, the study coordinator will administer the NMSS, the MDS-UPDRS parts II and IV as well as the modified MDS-UPDRS part III. They will also administer the MoCA, the MRI safety screening as well as a Device usability questionnaire. Participants will then be asked to completed the (PROs) including the Geriatric Depression Scale (GDS), the Parkinson's Anxiety Scale (PAS), the Epworth Sleepiness Scale (ESS), the Functional Assessment of Chronic Illness Therapy – Fatigue (FACIT-F) and the Device Usability Questionnaire and to bring them to their scheduled imaging visit. Participants will also be told to bring their Devices with them to the next clinic but that they should continue with twice daily treatments until their imaging visit.

End of treatment visit (in clinic)- week 12, 1 day after remote visit:

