Packets containing 4 sealed envelopes with the printed bar codes for randomization assignments will be provided by the Device sponsor. Each batch will contain two stimulation 1 and two stimulation 2 assignments. The envelopes will be randomly shuffled by an agent not involved with the study. A given packet will be completed before the next packet is opened. The device-training coordinator will load the treatment onto the device, will record the device number allocated to the participant and will train the participant according to the training script provided (see Study Coordinator Quick Reference Guide). If the participant makes a comment about feeling warming or cooling sensations that may potentially unblind the study staff to treatment allocation, this information is not to be shared with other study staff including other coordinators, the principal investigator, Device sponsor CRA, data analysts or the study statistician. All assessments will be performed by a study coordinator that does not take part in the interim phone calls. Participants will be told that pain should not be associated with treatment, and if they do experience pain, that they should stop treatment and contact the coordinator immediately and/or seek medical attention if necessary. However, they will also be told that in the absence of pain, for the integrity of the trial, they should not discuss their treatment experience with anyone associated with the study (e.g. other research staff, their caregiver or other people they may know are participating in the trial). The exception being when they are specifically asked about their treatment experience in the Device Usability Questionnaire at the end of the treatment period.

Unblinding at the study site will only occur in the case of a SADE (serious adverse event at least possibly related to the device) or UADE (serious and unanticipated/unexpected adverse events at least possibly related to the device) that also requires cessation of device treatment. If this situation seems likely, the Unblinding Investigator, noted in the Delegation of Authority Log, should contact SNS to request approval to unblind. Upon receipt of written permission from the

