Therapeutic CVS has been studied for use in prevention of episodic migraine and in treatment of symptoms of Parkinson's Disease. Results of these studies (including one multisite RCT and one single-site RCT, respectively), resulted in neither serious nor unanticipated/unexpected adverse events related to the study device. Additionally, there was no reduction in balance and no negative change in either mood or cognition.

The following AEs are known, possible side effects of using the investigational device:

More likely:

- Drowsiness
- Dizziness (whirling or spinning sensation; may also be called “giddiness” or vertigo)
- Treatment site discomfort (skin itching, skin irritation felt within the ear canal or around the ear canal or pressure felt within ear canal)

Less likely:

- Nausea
- Vomiting
- Tinnitus
- Headache

All of the potential AEs noted above are expected to resolve soon after use of the investigational device is stopped.

Serious Adverse Device Effect (SADE):

Adverse device effect that has resulted in any of the consequences characteristic of a serious adverse event.

Unanticipated Adverse Device Effect (UADE):

An Unanticipated Adverse Device Effect is a *serious* adverse effect on health or safety or any life-threatening problem or death caused by, or associated with, a device, if that effect, problem, or death was not previously identified in nature, severity, or degree of incidence in the investigational plan or application (including a supplementary plan or application), or any other unanticipated serious problem associated with a device that relates to the rights, safety, or welfare of subjects.

Procedures for AEs

- **Documentation and assessment**

- Following the informed consent process, clinical study participants will be routinely monitored for AEs at study visits and during telephone contacts from the clinical research staff. All AEs, regardless of treatment group, severity or suspected causal relationship to the investigational device, will be recorded on the participants’ source documentation.
- For all AEs, sufficient information will be obtained as to 1) determine the severity of the event (i.e., whether the event should be classified as “*serious*”); 2) assess the causal relationship between the adverse event and the investigational device; and 3) determine the outcome of the event.
- AEs will be followed until the event (or its sequelae) resolves or stabilizes at a level acceptable to the investigator and Device sponsor.

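### The instruction not to discuss treatment experience has no stated exception for adverse-event reporting; it conflicts with the protocol's safety procedures and may discourage reports of painless side effects

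*Combined protocol and SAP*

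**What the plan says.** The instruction stands in the section Randomization, Blinding and Unblinding. Participants are first told that treatment should not hurt and that, "if they do experience pain, that they should stop treatment and contact the coordinator immediately and/or seek medical attention if necessary". The next instruction reads: "in the absence of pain, for the integrity of the trial, they should not discuss their treatment experience with anyone associated with the study". The examples that follow are other research staff, the caregiver, and other people known to be taking part. One exception is written: "The exception being when they are specifically asked about their treatment experience in the Device Usability Questionnaire at the end of the treatment period".

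Elsewhere the protocol asks for AEs without limiting them to pain:

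- **Screening visit.** A handout with staff contact details, for use with questions or any AE, is reviewed with the participant.
- **Interim phone calls.** At weeks 3, 6 and 9 "the coordinator will ask about any adverse events". Participants also hold the site coordinator's contact details "so that they may report potential adverse events or issues with the Device in real time".
- **Procedures for AEs.** Participants are monitored for AEs at visits and telephone contacts, and every AE is recorded whatever the arm, severity or presumed cause.
- **Adverse Device Effect (ADE).** A list is introduced with "The following AEs are known, possible side effects of using the investigational device". It names drowsiness, dizziness and treatment site discomfort as more likely, and nausea, vomiting, tinnitus and headache as less likely.

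**The concern.** A participant who becomes dizzy or hears ringing during sessions has two instructions that do not fit together. The safety procedures say to report it. The blinding section, read literally, says not to mention a painless treatment experience, and gives the integrity of the trial as the reason. The same section adds that the trial's success depends on participants' willingness to take part blinded, which gives the silence rule some weight. Participants are also not told that the device works through ear temperature, so they may find it hard to separate a sensation that threatens the blind from a symptom that ought to be reported.

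At stake is the completeness of the safety record. Treatment is self-administered at home, so AE capture relies on what participants say. The study partner or caregiver, who must consent and take part, is named among those not to be told. No data safety monitoring board is planned; the sponsor and the site investigator review the AEs that reach them.

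**Working it through.** The plan states no figure on this point, so the check sets the passages side by side, with a few counts.

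**1. Which listed side effects fall under the silence rule?** The list under Adverse Device Effect has seven items.

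| Item | Pain? |
|---|---|
| Drowsiness | No |
| Dizziness | No |
| Nausea | No |
| Vomiting | No |
| Tinnitus | No |
| Treatment site discomfort | Borderline |
| Headache | Yes |

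The borderline item is worded as "Treatment site discomfort (skin itching, skin irritation felt within the ear canal or around the ear canal or pressure felt within ear canal", which does not use the word pain. So 5 of 7 are plainly not pain, or 5 + 1 = 6 of 7 if site discomfort is counted as not pain. These are counts of list items, not incidences.

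**2. Is AE reporting exempted anywhere?** The instruction has a carve-out for pain and an exception for the usability questionnaire. Neither covers a painless AE. The screening, interim-call and AE-procedure text does not mention the instruction, so nothing visible says which prevails.

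**3. Who is covered?** The rule says anyone associated with the study, but its first example is *other* research staff, shortly after the participant has been directed to the coordinator. Whether the coordinator who takes AE reports is inside or outside the rule is unclear. The caregiver is clearly inside it.

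**4. How long are the unsolicited stretches?** The calls that ask about AEs come at weeks 3, 6 and 9, and the end-of-treatment visit at week 12. Each interval is 3 weeks: 21 days × 2 treatments per day = 42 treatments. The whole period is 84 × 2 = 168 treatments; with the optional extension of about 2 weeks it is (84 + 14) × 2 = 196. These figures measure exposure, not lost reports. A spontaneous report is the only route between calls, and there the instruction has most room to act.

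**5. Could any loss differ by arm?** Under Description of Study Intervention, stimulation 1 delivers powered warm and cold waveforms. Stimulation 2 delivers no power and gives the least stimulation the device allows. Vestibular symptoms would be expected mainly under stimulation 1. This is an inference; the documents give no rates by arm. For scale, up to 20 participants at 1:1 is 20 / 2 = 10 per arm, so one participant whose symptom went unreported would move that arm's AE proportion by 1 / 10 = 10 percentage points at full enrolment.

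**The case against.** The strongest reply is that the rule concerns blinding, not safety. It sits close to text on warming or cooling remarks that could unblind staff, it speaks of treatment experience rather than AEs, and the safety sections keep their own vocabulary. A natural reading is that participants should not volunteer what a session feels like. AEs are actively asked about at three calls and monitored at visits, and a real-time route exists. What participants actually hear is in the training script, the Quick Reference Guide, the handouts and the consent form, none of which can be read here and any of which may already say that side effects are to be reported.

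Most of this stands, and it rules out three stronger readings that a reader might infer:

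- *Painless side effects would first come to light at week 12.* This requires the blinding section to override every AE procedure. The calls at weeks 3, 6 and 9 contradict it. The questionnaire is the only exception in that section, not the only occasion for reporting in the protocol.
- *The instruction suppresses reporting.* The documents show a conflict that may discourage reports. They contain no evidence that reports are lost.
- *The trial will understate the AE difference between arms.* The Analysis Plan specifies no between-arm AE comparison, and unequal loss is only an inference.

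The caregiver's role as a contact also comes from the missed-visit procedure, not from an AE-reporting duty, so harm by that route is not shown.

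The reply does not remove the conflict. A participant asked about AEs at a call still holds an instruction with no AE exemption, and a benign reading is not the only one available.

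**Conclusion.** The point holds as a conflict between instructions that carries a risk of under-reporting. Read literally, the silence rule covers 5 to 6 of the 7 side effects the protocol itself lists, while the screening, interim-call and AE sections ask for all of them to be reported. Scheduled questioning limits the harm, so the exposure is mainly spontaneous reports of painless symptoms in the three-week stretches between AE questions. The number of reports that might be lost cannot be estimated from the documents, and a heavier loss under stimulation 1 is plausible but not shown.

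The conclusion rests on two assumptions: that some participants would take a symptom felt during treatment to be part of their treatment experience, and that the participant materials do not already resolve the matter. The point concerns the safety record and does not bear on the imaging endpoints. It should be corrected because the correction is cheap.

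**What to change.** Reconcile the blinding section with the screening, interim-call and AE sections:

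- State that the non-discussion rule covers thermal or other device sensations and guesses about the stimulation pattern.
- State that it does not apply to reporting any unwanted symptom, painful or not, to the non-assessing coordinator, at any time or when asked, or to telling the caregiver about it.
- Name AE reporting as an exception beside the usability questionnaire.
- Make the same change in the training script and handout if they repeat the rule. The protocol withholds from participants that the device works by temperature, so these should speak of device sensations in general and not name warming or cooling.

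The existing pain instruction is not part of this change.

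The cost is a few sentences. The small downside is that the coordinator who hears about symptoms may infer the allocation. The protocol already bars interim callers from doing assessments and forbids passing on potentially unblinding comments. It does not say that real-time reports go to someone who does no assessments, so the new wording should.

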Secondary Objectives: To test hypothesis that 12-weeks of BID tvCVS treatments increase functional connectivity in the brain.

Exploratory Objectives: This study will seek to establish the relationships between changes in cerebral perfusion and CVR with improvements in clinical endpoints and to evaluate whether these changes are durable (at an assessment five weeks after the cessation of treatments). Furthermore, the feasibility of detecting change in cerebrovascular reactivity (CVR) as assessed via transcranial Doppler sonography (TCD) will also be explored as well as pulse wave velocity (PWV).

Study Design

A double-blinded, randomized trial comparing two different neurostimulation patterns will explore the effects of tvCVS treatments on changes in biomarkers of neurovascular status (i.e. cerebral blood flow perfusion and cerebrovascular reactivity) as well as their relationship to clinical endpoints. Eligible and enrolled participants will be randomly allocated in a 1:1 ratio using block randomization by the clinical site. Participants will be trained in the clinic to self-administer device treatment and then will continue to self-administer the ~19-minute treatments twice daily for 12 weeks in the home. Individual stimulation sessions will be spaced a minimum of 1 hour apart. Outcome measures will be administered at the baseline, the end of the 12-week treatment period and at 5 weeks post-treatment. Study participants will continue to take their approved PD medications throughout the study and will maintain patterns of usage throughout.

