Participants will be screened for COVID-19 upon arrival to the clinic. A bilateral ear exam will then be performed. A pregnancy test will be performed for all female participants of childbearing age. The MDS-UPDRS part III and the Timed Up and Go (TUG) will then be administered. Participants will then undergo the Magnetic Resonance Imaging (MRI) protocol (see below) and the transcranial Doppler sonography recordings of a hypercapnia challenge. Pulse wave velocity may be measured at this time.

After the collection of baseline neuroimaging data, participants will return to the clinic where they and their caregivers will try on an unpowered Device, will be randomized and trained on the use and care of the tvCVS Device. The Device will be allocated to the participant and the coordinator should note the Device ID in the Device Inventory Control Log. The study coordinator will assist the participant in adjustment of the headset settings. See Clinical Coordinator Quick Reference Guide for procedures. Once the participant confirms that the headset is comfortable enough to proceed, the participant will be randomized by selecting an envelope with printed bar code from the pack of four. Note that a given pack of 4 should be completed before a new pack is opened. The study coordinator will load the prescription on the Device and then place the unopened envelope in the study binder. * Envelopes should be only be opened under circumstances where treatment allocation must be known for management of an adverse event. Once the Participant has demonstrated proficiency in Device care and use procedures, they will take their designated Device home and will self-administer treatments twice daily during the treatment period. Participants will also be provided with a detailed handout (step-by-step guide with pictures), for self-administration of device treatments. Coordinators will also call the participant the next day to confirm that the participant was able to

administer treatments. If necessary, additional training sessions via telemedicine may be scheduled.

MRI protocol:

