Participants will be screened for COVID-19 upon arrival to the clinic. Effort should be made to schedule the imaging visit within 24 hours of the virtual visit. On arrival, the MDS-UPDRS part III and the Timed Up and Go (TUG) will then be administered. The bilateral ear exam will be performed. Participants will then undergo the Magnetic Resonance Imaging (MRI) protocol and the transcranial Doppler sonography recordings of a hypercapnia challenge outlined above. Pulse wave velocity may be measured at the time of the transcranial Doppler sonography recordings. The PROs will be collected and checked for completeness. Participants will be asked to complete missing items or complete in full in the clinic if forms were left at home. Devices will be collected. The Inventory Control Log should be updated noting the return date of the Device. The Device should then be returned to Robling with a completed Device Return Form. **Should participants forget to bring their TNM™ Device to this visit, they will be provided with an addressed pre-paid FedEx box that can be used to ship the Device directly back to Robling. Coordinators should check tracking information and follow up with reminder phone calls to ensure return of the Device.

Follow up visit (remote) – week 17:

During this remote visit, the study coordinator will administer the NMSS, the MDS-UPDRS parts II and IV as well as the modified MDS-UPDRS part III. They will also administer the MoCA, the MRI safety screening. Participants will then be asked to complete the (PROs) including the Geriatric Depression Scale (GDS), the Parkinson's Anxiety Scale (PAS), the Epworth Sleepiness Scale (ESS) and the Functional Assessment of Chronic Illness Therapy – Fatigue (FACIT-F) and to bring them to their scheduled imaging visit.

Follow up visit (in clinic)- week 17, 1 day after remote visit:

Participants will be screened for COVID-19 upon arrival to the clinic. Effort should be made to schedule the imaging visit within 24 hours of the virtual visit. On arrival, the MDS-UPDRS part III and the Timed Up and Go (TUG) will then be administered. Participants will then undergo the Magnetic Resonance Imaging (MRI) protocol. A bilateral ear exam will only be performed if there were residual ear-related AEs at the last treatment visit.

SCHEDULE OF ACTIVITIES

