- Must have ability to reliably use the investigational device
- Must be able to understand and complete all assessments (provided in English only) within a given on-state period
- Must be willing and able to undertake a 1-hour imaging session in an MRI magnet with a head coil in place during 3 separate clinic visits and a 1-hour imaging session using transcranial Doppler sonography during 2 separate clinic visits
- Must have a study partner and/or regular caregiver (defined as someone who sees the participant for more than one hour a day, 3x per week) that is willing to consent and participate in the trial
- Must have access and capability to complete assessments using telemedicine platforms
- Must demonstrate moderate burden of motor symptoms and non-motor symptoms in PD (MDS-UPDRS part II ≥ 9 and MDS-UPDRS part I scores ≥ 9)
- Must consent to being videotaped during motor examination visit
- Must be willing to answer questions related to sexual interest, arousal and performance in an interview with study staff

Exclusion Criteria:

- Participant anticipates being unable to attend all study visits and complete all study activities during the clinical trial
- Women of child-bearing potential who are pregnant or plan to become pregnant during the course of the study
 - Women of child-bearing potential (i.e., are not yet 3 years removed from their first menopausal symptom), who are not abstinent or exclusively in same sex relationships must:
 - test negative for pregnancy as indicated by a negative urine pregnancy test

- agree to use an approved contraception method listed in the section **Concomitant Medications** for the entirety of the study
- Have experienced a myocardial infarction, angina or stroke within the past 12 months,
- Use of medications that regulate heart rate
- Have a history or prior diagnosis of dementia or adjusted score ≤ 20 on the Montreal Cognitive Assessment at the baseline visit. This exclusion criterion has been set specifically to improve the validity of scores assessed from the scaled questionnaires rather than reflecting a concern about safety for this population.
- Those receiving deep brain stimulation therapy
- Treated with a pump for continuous delivery of DRT (Dopamine replacement therapy)
- Use of Apomorphine rescue
- Works night shifts

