AEs will be summarized by the Device sponsor CRA. Device sponsor management and the site PI will regularly convene to monitor and review AE reports. All AEs will be evaluated on an individual basis to determine whether the occurrence may be related to device use. Should a serious adverse event (SAE) occur that is deemed to be likely related to device use, the potential for the universality will be assessed within 48 hours. If evidence suggests that treatments with the device could create a safety concern for participants, the study Device sponsor will be pause or stop the study early, as appropriate.

It should be noted that the above scenario is considered to be highly unlikely. The device has been designated as NSR by the FDA, and there were no reports of significant or unexpected AEs

that were potentially related to device in either the PD single-site RCT or the episodic migraine RCT.

Participant Discontinuation/Withdrawal from the Study:

Withdrawal Criteria

Study participants must be withdrawn from the clinical trial if any of the following events occur:

- the participant is significantly and willfully non-adherent to the requirements of the protocol (principal investigator & Device Sponsor decision),
- the participant develops an illness (adverse event) that would interfere with his/her continued participation,
- the participant withdraws his/her consent,
- the principal investigator feels that it is the participant's best interest to be withdrawn,
- SNS discontinues the study or has achieved the targeted enrollment

If the study participant is discontinued from the participation in the study for any reason, the principal investigator must make every effort to perform all evaluations for the final visit, collect the device from the participant (if it is still within their possession) and document the reasons for discontinuation. If the participant withdraws from the study due to an adverse event that is potentially related to use of the device, the coordinator should continue to follow up with the participant at regular intervals, and at least every two weeks until the AE resolves or until the participant withdraws consent for the follow-up procedure. Reasons for study withdrawal should be documented on the subject disposition form.

Lost to Follow-up

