A voluntarily signed and dated informed consent, approved by the IRB, will be obtained from each study participant prior to involvement in any study-related activity. If the potential participant is recruited in the clinic, the participant will be given the opportunity to review the informed consent form (ICF) and ask questions relating to its content in a private room. Study staff will verify that potential participants understand the content of the ICF and will witness the signature. Potential study participants should also be afforded the opportunity to take the consent form home, prior to signing, and discuss with family members, as needed. In this case, potential participants will be told to call the phone number listed on the ICF to schedule a remote visit if they decide they are interested in participating and will also be told to hold off on signing the ICF until the remote screening visit. Review, signature and dating the ICF will be the first task completed during the remote screening visit. The PI or designee witnessing the signature should request that the participants hold up the ICF on the video (using a HIPAA compliant platform such as WebEx), and a screen shot will be taken and saved within the study records. Participants will be asked to mail their ICF to the site using a pre-addressed stamped envelope provided by WFU. Potential participants who demonstrate eligibility and are enrolled in the study will be given a copy of the signed consent form at their baseline clinic visit. For screen failures, a copy of the signed consent form will be returned via mail.

Confidentiality and Privacy

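### The mandatory withdrawal rule for reaching target enrolment is not limited to people not yet randomised, so as written it conflicts with the 12-week treatment and the week-12 and week-17 visits (minor)

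*Combined protocol and SAP*

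**What the plan says.** Under Participant Discontinuation/Withdrawal from the Study, the Withdrawal Criteria open with "Study participants must be withdrawn from the clinical trial if any of the following events occur". The last item in the list is "SNS discontinues the study or has achieved the targeted enrollment". No qualifier follows it.

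The rest of the protocol sets out a fixed course for each randomised participant:

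- Study Design: "Outcome measures will be administered at the baseline, the end of the 12-week treatment period and at 5 weeks post-treatment".
- Treatment period: twice-daily treatment continues until the end-of-treatment clinic visit.
- Description of Study Intervention: the stimulation schedule runs for 84 days.
- The visit descriptions include "Follow up visit (in clinic)- week 17, 1 day after remote visit".
- Inclusion Criteria: participants must accept a one-hour "imaging session in an MRI magnet with a head coil in place during 3 separate clinic visits".

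The Sample size text gives a ceiling of 20 enrolled and a cap of 4 per month. It names no separate target.

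**The concern.** The item is written as an obligation, and any one listed event is enough to trigger it. Meeting the enrolment target is an expected milestone in a trial that goes to plan. A rule that withdraws participants at that point would end treatment and follow-up for anyone who has not yet completed them.

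If the rule were followed, those participants would miss the end-of-treatment imaging that carries the primary objectives, the five-week durability assessment, or both. With a ceiling of 20 participants, even a few such losses would matter.

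**Working it through.** The protocol states no figure that can be reproduced here. The check is a comparison of texts, followed by a count for scale.

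**1. Does the list cover randomised people?** Yes, taken as a whole. The paragraph after the list tells the investigator to attempt the final-visit evaluations and to retrieve the device if the participant still has it. Devices are issued only at the baseline imaging and device training visit, where randomisation also takes place: "Once the participant confirms that the headset is comfortable enough to proceed, the participant will be randomized by selecting an envelope". Other items, such as wilful non-adherence, plainly concern people on treatment.

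**2. Does any other text narrow the item?** None was found.

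**3. Does the clause have a legitimate use?** Yes. Consent "will be obtained from each study participant prior to involvement in any study-related activity", and randomisation comes only after baseline imaging. Someone may therefore be consented but unrandomised when the places are filled. The defect is the missing qualifier.

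**4. Is the conflict independent of accrual?** Yes, provided the target is reached. On the day the target is met, the person who completes it has 0 days of follow-up, which is less than both 84 days (12 × 7) and 119 days (17 × 7). At least one participant is always caught.

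**5. How many more could be caught?** Inputs from the protocol are 20 enrolled, at most 4 per month, and assessments at 84 and 119 days. Assumed are even spacing, a month of 30.4 days, and every accrual rate used.

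The k-th most recent participant (k = 0 to 19) has been enrolled for k × 30.4 / rate days. The number short of a visit is the number of k for which this is below 84 or 119.

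| Assumed rate per month | Spacing (days) | 84 / spacing | Short of week 12 | 119 / spacing | Short of week 17 |
|---|---|---|---|---|---|
| 4 | 7.6 | 11.05 | 12 (k = 0–11) | 15.66 | 16 (k = 0–15) |
| 3 | 10.13 | 8.29 | 9 (k = 0–8) | 11.74 | 12 (k = 0–11) |
| 2 | 15.2 | 5.53 | 6 (k = 0–5) | 7.83 | 8 (k = 0–7) |
| 1 | 30.4 | 2.76 | 3 (k = 0–2) | 3.91 | 4 (k = 0–3) |
| 0.25 | 121.6 | 0.69 | 1 (k = 0) | 0.98 | 1 (k = 0) |

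Sensitivity:

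- Enrolling in batches at the start of each month gives the same counts, except 8 and 11 at 3 per month.
- A month of 28 to 31 days changes the counts at 4 per month to 11–12 and 16–17.
- A target of 16 instead of 20 changes nothing. A target of 12 changes only the week-17 count at 4 per month, to 12.
- The clock here starts at enrolment. Treatment starts later, at the training visit, so time on treatment is never longer than time since enrolment. For a given accrual pattern, starting the clock at training could only raise the counts.
- Adding the optional extension of about two weeks to both time points gives 13 and 18 at 4 per month, and 4 and 5 at 1 per month.

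**The case against.** The strongest reply is that no one would read the item this way. The protocol uses the term for study participants loosely: the Informed Consent section applies it to people who have not yet consented, and the Lost to Follow-up definition adds that they be enrolled and participating. The instruction to retrieve the device allows for people who have none. The item therefore has a natural target, namely people in screening when places run out. The specific operating text on treatment and visits points the same way, and no credible route to lost data, bias or harm remains.

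Most of this stands as an argument about weight. It shows what was probably intended. It does not supply the missing words, and a mandatory rule should not depend on the site disregarding it. The duty to attempt final-visit evaluations softens the effect, but an early final visit is not a week-12 or week-17 assessment.

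Two narrower objections are fair. The protocol gives a ceiling and no stated target, so the loss of at least one participant is conditional on a target being reached. The accrual counts rest on assumed rates; they show the reach of the wording and should not be read as a forecast.

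**Conclusion.** The inconsistency is real and minor. As written, the rule gives the wrong instruction for randomised participants. Whenever the target is reached it catches at least 1 participant. Under assumed even accrual of 20 people at 1 to 4 per month, it catches 3 to 12 before week 12 and 4 to 16 before week 17. It never operates if accrual stops short of the target.

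The site is unlikely to apply it, and no analysis method, allocation procedure, endpoint definition or sample-size figure depends on it. The counts do not justify a higher priority than an optional correction.

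**What to change.** Qualify the item and keep it. Suggested wording: *SNS discontinues the study or, for consented participants not yet randomised, the targeted number of participants has been randomised.*

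The trigger should be the number randomised, because Study Design places enrolment first: "Eligible and enrolled participants will be randomly allocated in a 1:1 ratio". A trigger on enrolment would also catch the last enrolled person before randomisation. Since Sample size gives only a ceiling on enrolment, that section should also say what number randomised is meant.

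Add one sentence to Sample size: all randomised participants continue to week 17 whether or not enrolment has closed.

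The cost is one qualifier and a short addition to Sample size. The clause's legitimate use is kept, and the number of randomised participants withdrawn on reaching the target becomes 0.
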